### **6.1.3 Lack of Efficacy or Worsening of Disease Under Study**

Events that are clearly consistent with the expected pattern of progression of the underlying disease are also considered an expected outcome for this study and will be captured as adverse events, but will not be subject to expedited reporting. These data will be captured as efficacy assessment data only. Refer to [Appendix F](#) for listing of events expected with progression of ED SCLC.

#### **6.1.4 Serious Adverse Events**

If an adverse event meets any of the following criteria, it is to be reported to AbbVie as a serious adverse event (SAE) within 24 hours of the site being made aware of the serious adverse event:

Death of Subject	An event that results in the death of a subject.
Life-Threatening	An event that, in the opinion of the investigator, would have resulted in immediate fatality if medical intervention had not been taken. This does not include an event that would have been fatal if it had occurred in a more severe form.
Hospitalization or Prolongation of Hospitalization	An event that results in an admission to the hospital for any length of time or prolongs the subject's hospital stay. This does not include an emergency room visit or admission to an outpatient facility.
Congenital Anomaly	An anomaly detected at or after birth, or any anomaly that results in fetal loss.
Persistent or Significant Disability/Incapacity	An event that results in a condition that substantially interferes with the activities of daily living of a study subject. Disability is not intended to include experiences of relatively minor medical significance such as headache, nausea, vomiting, diarrhea, influenza, and accidental trauma (e.g., sprained ankle).

**Important Medical Event Requiring Medical or Surgical Intervention to Prevent Serious Outcome**

An important medical event that may not be immediately life-threatening or result in death or hospitalization, but based on medical judgment may jeopardize the subject and may require medical or surgical intervention to prevent any of the outcomes listed above (i.e., death of subject, life-threatening, hospitalization, prolongation of hospitalization, congenital anomaly, or persistent or significant disability/incapacity). Additionally, any elective or spontaneous abortion or stillbirth is considered an important medical event. Examples of such events include allergic bronchospasm requiring intensive treatment in an emergency room or at home, blood dyscrasias or convulsions that do not result in inpatient hospitalization, or the development of drug dependency or drug abuse.

For serious adverse events with the outcome of death, the date and cause of death will be recorded on the appropriate case report form.

**6.2 Adverse Events Expected Due to SCLC or Progression of SCLC**

Adverse events that may be expected from primary SCLC lesions, compression of adjacent thoracic structures or distant metastases are presented in [Appendix F](#) of the protocol.

These adverse events may occur alone or in various combinations and are considered expected adverse events in SCLC subjects but will not be subject to expedited reporting. These data will be captured as efficacy assessment data only.

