### **3.3.3 Veliparib Clinical Studies**

Veliparib is being investigated in AbbVie-sponsored studies, in Investigator initiated studies (IIS), and in CTEP-sponsored studies. In these studies, veliparib is administered as monotherapy, combined with a variety of chemotherapeutic agents, or combined with radiation therapy.

Summary preliminary or final efficacy data from AbbVie sponsored studies show that veliparib has activity in combination with temozolomide (TMZ), with radiotherapy, and with carboplatin + paclitaxel. Data from non-AbbVie sponsored studies show veliparib has activity as monotherapy for treatment of ovarian cancer and activity in combination with carboplatin + paclitaxel for treatment of early breast cancer. Veliparib is currently in Phase 2 and Phase 3 clinical development in combination with several DNA-damaging agents across a variety of cancer indications.

Several clinical studies explored combinations of veliparib with carboplatin-based combination chemotherapies and one study is evaluating cisplatin/etoposide/veliparib combination.

Phase 1 data from subjects treated with veliparib, carboplatin, and paclitaxel for advanced non-small cell lung cancer (NSCLC) are available from Cancer Therapy Evaluation Program (CTEP) Study 7967. Veliparib was given orally BID on Days 1 to 7 of each 21-day cycle, and paclitaxel and carboplatin were administered on Day 3. Two DLTs

(febrile neutropenia and hyponatremia) were observed in 2 of 7 evaluable subjects treated at the maximum tolerated dose of veliparib 120 mg BID, paclitaxel 200 mg/m^2, and carboplatin AUC 6. The most common AEs reported in this study were neutropenia and fatigue (reported in > 50% of subjects); nausea, thrombocytopenia, and peripheral sensory neuropathy (> 40% of subjects); and anemia, constipation, alopecia, diarrhea, decreased appetite, lymphopenia, and myalgia (> 20% of subjects).

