## **6.5 Adverse Event Collection Period**

[figure not shown]
All protocol related serious adverse events and nonserious adverse events must be collected from the signing of the study specific informed consent until study drug administration.

In addition, all adverse events reported from the time of study drug administration until 30 days following discontinuation of study drug administration have elapsed will be collected, whether solicited or spontaneously reported by the subject.

Serious and nonserious adverse events occurring after the study specific informed consent is signed but prior to the initial dose of study drugs will be collected only if they are considered by the Investigator to be causally related to the study-required procedures.

Adverse event information will be collected as shown in [Figure 4](#).

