### Preferred Term (MedDRA Version 13.1)

---

Pleural effusion  
Malignant pleural effusion  
Metastases to pleura  
Dyspnoea  
Cough  
Non-cardiac chest pain  
Haemoptysis\*  
Oesophageal obstruction  
Pneumonia\*  
Vocal cord paralysis  
Dysphonia  
Dysphagia  
Superior vena cava syndrome  
Horner's syndrome  
Metastases to bone  
Metastases to lymph nodes  
Metastases to liver  
Metastases to spine  
Metastases to the mediastinum  
Metastases to pleura  
Metastases to adrenals  
Metastases to meninges  
Metastases to central nervous system  
Metastatic pain  
Cancer pain  
Tumour pain  
Fatigue  
Asthenia  
Pulmonary embolism\*  
Blood Antidiuretic Hormonal Abnormal (SIADH)  
Cushing's syndrome  
Cachexia  
Shock\*  
Septic shock\*

---

---

Deep vein thrombosis\*  
Lower respiratory tract infection\*  
Respiratory tract infection\*  
Upper respiratory tract infection\*  
Opportunistic infection\*  
Viral infection\*  
Fungal infection\*  
Bacterial infection\*  
Pulmonary haemorrhage\*  
Lung abscess\*  
Empyema\*  
Sepsis\*  
Lymphadenopathy  
Decreased appetite  
Malaise  
Weight decreased  
Headache  
Pain excluding chest pain  
Pyrexia

---

\* Includes life threatening or fatal events.

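### Protocol 6.2 and 6.1.3 route Appendix F events, including infections and fatigue, to efficacy data only, which contradicts the protocol's own adverse event recording rules

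*Protocol*

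**What the plan says.** Section 6.2 of the Protocol introduces the list in Appendix F: "Adverse events that may be expected from primary SCLC lesions, compression of adjacent thoracic structures or distant metastases are presented in" that appendix. It says these events "are considered expected adverse events in SCLC subjects but will not be subject to expedited reporting", and closes with "These data will be captured as efficacy assessment data only". It attaches no condition on causality, grade or seriousness. Appendix G shows that the current amendment added the efficacy-only sentence to 6.2, so it is not leftover text.

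Section 6.1.3 concerns "Events that are clearly consistent with the expected pattern of progression of the underlying disease". It says that these "will be captured as adverse events, but will not be subject to expedited reporting"; its next sentence then restricts them to efficacy data.

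Section 6.5 says that "all adverse events reported from the time of study drug administration until 30 days following discontinuation of study drug administration" have elapsed will be collected. Appendix F marks some of its terms with an asterisk, explained as "Includes life threatening or fatal events".

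**The concern.** A site cannot record an event as an adverse event and also record it as efficacy data only. The conflict matters because Appendix F is not confined to tumour symptoms. It names general infection terms, sepsis and septic shock, together with fatigue, decreased appetite and pyrexia. Any of these can also result from treatment.

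Protocol 3.3.3 supports the treatment link directly for two terms. In an earlier Phase 1 study of veliparib with carboplatin and paclitaxel, the commonest adverse events included "neutropenia and fatigue (reported in > 50% of subjects", and decreased appetite exceeded 20%. For the infections the link is an inference: the same section says that Grade 3 or 4 cytopenias may occur when veliparib is combined with cytotoxic chemotherapy.

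Further evaluation of safety is a stated Phase 2 secondary objective. The TEAE and SAE tables (Protocol 8.1.7.2 and 8.1.7.3, SAP 11.2) and much of the DMC's review list (SAP 14.1.3.1) are built from adverse event records. Neither plan can recover an event that was never entered, and the drug-by-drug causality assessment required by Protocol 6.4 would be lost with it.

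**Working it through.** There is no planned figure to reproduce. The check is a comparison of the recording rules, a count of Appendix F, and a statement of what can be said about size.

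**1. The rules side by side**

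| Place | Instruction for an Appendix F event on treatment |
|---|---|
| Protocol 6.2 | Efficacy data only; no expedited reporting |
| Protocol 6.1.3, first sentence | Adverse event; no expedited reporting (if clearly consistent with progression) |
| Protocol 6.1.3, next sentence | Efficacy data only |
| Protocol 6.1.2 | On-study death not attributed solely to progression goes on the adverse event eCRF |
| Protocol 6.1.4 | Serious event goes to the sponsor within 24 hours; no Appendix F exemption |
| Protocol 6.5 | All adverse events to 30 days after study drug; no Appendix F exemption |
| Protocol 8.1.7.2, SAP 11.2 | Treatment-emergent events tabulated; no Appendix F term excluded |

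Take a fatal septic shock on treatment that the investigator does not attribute solely to progression. Sections 6.1.2 and 6.1.4 make it reportable. Section 6.2, read by its list, makes it efficacy data only.

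**2. Count of Appendix F**

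- Entries: 53, of which 52 are distinct (metastases to pleura appears twice).
- Asterisked: 17.
- Infections among the asterisked: 12, namely pneumonia, septic shock, sepsis, lower, upper and unspecified respiratory tract infection, opportunistic, viral, fungal and bacterial infection, lung abscess and empyema.
- Remaining asterisked terms: 17 − 12 = 5 (haemoptysis, pulmonary embolism, shock, deep vein thrombosis, pulmonary haemorrhage).

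**3. Whether efficacy data would use these events**

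The efficacy variables are PFS, ORR, OS, DOR and ECOG status (Protocol 5.3.3, SAP 10.3 and 10.6.4). PFS counts radiographic progression or death, and ORR rests on RECIST. A fatal event would count as a death in PFS and OS, but the sepsis, pneumonia or fatigue itself feeds no planned efficacy analysis.

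**4. Size and direction**

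Let p be the true event rate in an arm and k the share of events that reach the adverse event form. Then

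recorded difference = kA·pA − kC·pC.

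The documents give no k. With rates assumed purely for illustration, pA = 30% and pC = 10% (true difference 20 points):

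- kA = kC = 1: 30 − 10 = 20 points
- kA = kC = 0.75: 22.5 − 7.5 = 15 points
- kA = kC = 0.5: 15 − 5 = 10 points
- kA = kC = 0.25: 7.5 − 2.5 = 5 points
- kA = 0.25, kC = 0.75: 7.5 − 7.5 = 0 points
- kA = 1, kC = 0.5: 30 − 5 = 25 points

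The recorded difference can therefore be unchanged, smaller or larger than the true one, depending on quantities that the documents do not supply.

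**The case against.** The strongest reply is that 6.2 works by cause, not by preferred term. Its opening words tie the list to the tumour and its metastases, and 6.1.3 is limited to events clearly consistent with progression. On that reading, a neutropenic sepsis attributed to chemotherapy falls outside both sections and is recorded as usual. Sections 6.1.2, 6.1.4 and 6.5 support this. So does SAP 11.2, which splits events leading to discontinuation by whether they were due to progression and so presupposes progression-related events in the adverse event database. Section 6.6, on adverse event reporting, was not in the text available for this review and may clarify matters.

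Much of this stands. It shows that efficacy-only capture is one of several conflicting instructions and that loss from the tables is possible, not certain. It does not remove the conflict. Section 6.2 points sites to a list of terms with no causality test, and 6.1.3 contradicts itself even for events that clearly are progression.

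A reader might also infer that any loss falls mainly on the veliparib arms and so hides a safety difference. The documents do not support that. The high fatigue rate comes from an uncontrolled study. The randomised veliparib, carboplatin and paclitaxel trial described in Protocol 3.3.3 reports increases in leukopenia (under 15%) and neutropenia (under 10%), and none above 5% for any other adverse event. It used 120 mg BID around chemotherapy for 7 days, so it is not decisive for the present regimen. Phase 2 is double-blind, and every arm works under the same text. Neutropenia, febrile neutropenia, thrombocytopenia, anaemia, nausea and vomiting are not in Appendix F, and laboratory cytopenias are analysed separately (Protocol 8.1.7.6, SAP 11.4). Nor do the documents support any count of unrecorded subjects by arm: that would need assumed event rates and an assumed capture rate.

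**Conclusion.** The contradiction is real and sits in current protocol text. Section 6.2 and the second of the two sentences in 6.1.3 cannot be followed together with the rest of 6.1.3, 6.1.2, 6.1.4 and 6.5. A site that applies 6.2 literally could leave treatment-related events off the adverse event eCRF, including any of 17 terms flagged as potentially life-threatening or fatal. They would then be absent from the TEAE and SAE tables and the DMC outputs.

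This is a data-recording rule that should be corrected. It is not evidence that safety data have been lost. The conclusion rests on the wording alone and assumes that nothing in Section 6.6 overrides it. How many sites read 6.2 literally is unknown, so the size and direction of any effect on the arm comparisons are also unknown.

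**What to change.** Reconcile the passages as follows.

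- Delete the efficacy-only sentence from Protocol 6.1.3 and 6.2.
- State that Appendix F events are recorded on the adverse event eCRF with grade, seriousness and causality, and are included in the TEAE and SAE tables and in DMC outputs.
- Limit any exemption to expedited reporting, and say whether that means the sponsor's onward reporting only or also the 24-hour site report in 6.1.4.
- Check that Section 6.6 agrees.

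The text change is two deletions, a short statement and a site clarification. It asks for nothing beyond what 6.5 already requires.

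New wording will not recover events already omitted. The SAP is dated 15 November 2018, after the 14 September 2018 efficacy cutoff, and SAP 4.4 records that the DMC review was held in October 2017 with no further review thought necessary before database lock. For data already collected, sites should be queried about Appendix F events left off the adverse event form, and the study report should state which rule was applied. The site queries are the main cost. The change concerns recording only and alters no treatment rule.

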**6.3 Adverse Event Severity**

The investigator will rate the severity of each adverse event according to the National Cancer Institute Common Terminology Criteria for Adverse Events (NCI CTCAE Version 4.0).

For adverse events not captured by the NCI CTCAE Version 4.0, the investigator will use the following definitions to rate the severity of each adverse event:

Mild (Grade 1)	The adverse event is transient and easily tolerated by the subject.
Moderate (Grade 2)	The adverse event causes the subject discomfort and interrupts the subject's usual activities.
Severe (Grade 3/4)	The adverse event causes considerable interference with the subject's usual activities and may be incapacitating or life-threatening.
Death (Grade 5)	Death

If a reported adverse event increases in severity, the initial adverse event should be given an outcome date and a new adverse event should be reported to reflect the change in severity.

For all reported serious adverse events that increase in severity, the SAE supplemental eCRFs also need to be updated and need to include the new AE serial number.

#### **6.4 Relationship to Study Drug**

The investigator will use the following definitions to assess the relationship of the adverse event to the use of study drug:

Reasonable Possibility	After consideration of factors including timing of the event, biologic plausibility, clinical judgment, and potential alternative causes, there is sufficient evidence (information to suggest a causal relationship).
No Reasonable Possibility	After consideration of factors including timing of the event, biologic plausibility, clinical judgment and potential alternative causes there is insufficient evidence (information to suggest a causal relationship).

For causality assessments, events assessed as having a reasonable possibility of being related to the study drug will be considered "associated." Events assessed as having no reasonable possibility of being related to study drug will be considered "not associated." In addition, when the investigator has not reported a causality or deemed it not assessable, AbbVie will consider the event associated. For the purposes of this study, causality assessments will be attributed to veliparib/placebo or carboplatin or etoposide separately.

If an investigator's opinion of no reasonable possibility of being related to study drug is given, another cause of event must be provided by the investigator for the serious adverse event.

## **6.5 Adverse Event Collection Period**

[figure not shown]
All protocol related serious adverse events and nonserious adverse events must be collected from the signing of the study specific informed consent until study drug administration.

In addition, all adverse events reported from the time of study drug administration until 30 days following discontinuation of study drug administration have elapsed will be collected, whether solicited or spontaneously reported by the subject.

Serious and nonserious adverse events occurring after the study specific informed consent is signed but prior to the initial dose of study drugs will be collected only if they are considered by the Investigator to be causally related to the study-required procedures.

Adverse event information will be collected as shown in [Figure 4](#).

**Figure 4. Adverse Event Collection**

\* Only if considered by the Investigator to be causally related to study-required procedures.

## **6.7 Pregnancy**

In the event of a positive pregnancy test, subjects must immediately discontinue study drug and must be discontinued from the study. The investigator must report the positive pregnancy test to the appropriate contact listed in protocol Section 6.6 within 1 working day of the site becoming aware of the pregnancy.

All subjects should be informed that contraceptive measures should be taken throughout the study and for 6 months after discontinuing study drug. Information regarding a pregnancy occurrence in a study subject and the outcome of the pregnancy will be collected. The Investigator must follow the pregnancy to completion and provide an update to AbbVie after delivery.

Male subjects should be informed that contraceptive measures should be taken by their female partners. If the subject's partner should become pregnant during the study, this

should also be reported and data may be collected. In the event of pregnancy occurring in the partner of an enrolled subject, written informed consent for release of medical information from the partner must be obtained prior to the collection of any pregnancy-specific information and the pregnancy will be followed to outcome.

Pregnancy in a study subject is not considered an adverse event. However, the medical outcome of an elective or spontaneous abortion, stillbirth or congenital anomaly is considered a serious adverse event and must be reported to AbbVie within 24 hours of the site becoming aware of the event.

## **6.8 Dose Limiting Toxicities**

Dose limiting toxicities for Phase 1 dose escalation purposes will be determined during DLT observational period C1D-2 to pre-dose C2D1 in any of the dose-escalation cohorts, with grading according to the National Cancer Institute (NCI) Common Toxicity Criteria for Adverse Events (CTCAE), version 4.0. Any of the events described in Section 5.1 considered to have a reasonable possibility of being related to veliparib will be considered a dose limiting toxicity (DLT).

Subjects experiencing DLTs during the DLT observational period C1D-2 to pre-dose C2D1 will generally be discontinued from further participation in the study, but may continue at the same or a reduced dose with written approval by the Sponsor if there is evidence of clinical benefit.

### **6.8.1 Determination of the MTD**

If a single subject within a cohort experiences a DLT, a total of 6 subjects will be enrolled and dosed at the same dose level. If these additional subjects do not exhibit a DLT, dose escalation may proceed. If any of the additional subjects exhibits a dose limiting toxicity, then dose de-escalation may occur to interrogate lower dose levels. MTD, if identified, will be defined at the highest dose level at which less than 2 of 6 subjects or < 33% of (if cohort is expanded beyond 6) subjects experience a DLT. MTD may be determined independently for each veliparib dosing schedule.

### **6.8.2 Determination of the RPTD**

If an MTD is reached, the RPTD will not be a dose higher than the MTD and will be selected based on the types of DLTs which occur and the MTD identified. If an MTD is not reached, then the RPTD will be defined based on the safety and available PK data.

## **8.0 Statistical Methods and Determination of Sample Size**

### **8.1 Statistical and Analysis Plans**

For subjects in the Phase 1 portion, the date of enrollment is defined as the first day of study drug administration. For subjects in the randomized Phase 2 portion, the date of randomization (enrollment) is defined as the date that the IRT issued a subject number.

ORR will be performed on all dosed subjects in the Phase 1 portion of the study.

The primary, secondary, and tertiary efficacy analyses will be performed on all subjects in the randomized Phase 2 portion of the study.

Safety analyses will be performed separately for the Phase 1 and Phase 2 portions. All subjects who receive at least one dose of the study drug will be included in the safety analysis.

Unless otherwise noted, data will be summarized for Phase 1 and Phase 2 subjects separately.

